#### **11.2.2.5 Adverse Event Relationship to Investigational Product**

The Investigator must make an assessment of each AE's relationship to the IP. The categories for classifying the Investigator's opinion of the relationship are as follows:

Related            A reasonable possibility exists of a relationship between the AE and IP.

Not related        No reasonable possibility exists of a relationship between the AE and IP.

Medical judgment should be used to determine the relationship, considering all relevant factors, including pattern of reaction, temporal relationship, relevant medical history, and confounding factors such as co-medication or concurrent diseases.

#### **11.2.3 Documentation**

All AEs that occur within the period of observation for the study must be documented in the eCRF with the following information, where appropriate. (The period of observation for the study is described in Section 11.2).

- AE name or term
- When the AE first occurred (start date and time)
- When the AE stopped (stop date and time or an indication of "ongoing")
- Severity of the AE
- Seriousness (hospitalization, death, etc.)
- Actions taken
- Outcome
- Investigator opinion regarding the AE relationship to the IP

#### **11.2.4 Treatment of Adverse Events**

Adverse events that occur during the study will be treated, if necessary, by established standards of care. If such treatment constitutes a deviation from the protocol, the subject should be withdrawn from the study and the reason must be documented in the eCRF. The decision about whether the subject may continue in the study will be made by the sponsor after consultation with the Investigator and/or Medical Monitor.

If AEs occur in a subject that are not tolerable, the Investigator must decide whether to stop the subject's involvement in the study and/or treat the subject. Special procedures may be

recommended for the specific IP, such as the collection of a serum sample for determining blood concentrations of IP, specific tapering procedures, or treatment regimens, as appropriate.

### **11.2.5 Follow-up**

Any AE will be followed up to a satisfactory resolution, until it becomes stable, or until it can be explained by another known cause(s) (i.e., concurrent condition or medication) and clinical judgment indicates that further evaluation is not warranted. All findings relevant to the final outcome of an AE must be reported in the subject's medical record and recorded on the eCRF page.

### **11.2.6 Reporting**

#### **11.2.6.1 Serious Adverse Events**

The Investigator or designee must report all SAEs promptly to [REDACTED] within 24 hours of first becoming aware of the event by completing, signing, and dating the Serious Adverse Event Report Form, verifying the accuracy of the information recorded in the form with the source documents and eCRF, and sending the SAE Report Form to [REDACTED] by one of the following methods:

email: [REDACTED]

Fax number (back-up): [REDACTED]

This written report should be submitted on the SAE form provided for this purpose. At the time of first notification, the Investigator or designee should provide the following information, if available:

- Protocol number
- Reporter (study site and Investigator)
- Subject's study number
- Subject's date of birth
- Subject's gender
- Date of first dose of IP
- Date of last dose of IP, if applicable
- Adverse event term
- Date of occurrence of the event
- A brief description of the event, outcome to date, and any actions taken
- The seriousness criteria(on) that were met
- Concomitant medication at onset of the event
- Relevant medical history information

- Relevant laboratory test findings
- Investigator's opinion of the relationship to IP ("Is there a reasonable possibility that the IP caused the SAE? Yes or No?")
- Whether and when the Investigator was unblinded as to the subject's treatment assignment

Any missing or additional relevant follow-up information concerning the SAE should be sent to the sponsor/sponsor representative via the same contact details above as soon as possible, and within 7 days, on a follow-up SAE Report Form, together with the following minimal information (initial report, AE, date of occurrence, subject identification [ID], study ID, IP, and site number); this will allow the follow-up information to be linked to the initial SAE report.

Specific information may be requested by the [REDACTED] Pharmacovigilance Department using a follow-up request form sent via email communication.

The Investigator is required to comply with applicable regulations (including local laws and guidances) regarding the notification of his or her health authorities, IRB, principal and coordinating investigators, study investigators, and institutions. Each investigator is obligated to learn about the reporting requirements for investigators in his/her country. The study monitor may be able to assist with this.

### **11.2.6.2 Nonserious Adverse Events**

Nonserious AEs will be recorded in the eCRF and reported by [REDACTED] to the sponsor in accordance with the study-specific safety management plan.

## **11.3. Special Considerations**

### **11.3.1 Pregnancy**

All women of childbearing potential who participate in the study should be counseled on the need to practice adequate birth control and on the importance of avoiding pregnancy during study participation. Women should be instructed to contact the investigator or study staff immediately if pregnancy occurs or is suspected.

Pregnancy testing will be conducted prior to administration of the IP on every woman of childbearing potential. A woman who is found to be pregnant at the Screening visit will be excluded from the study and considered to be a screening failure.

A woman who becomes pregnant during IP treatment or within 14 days of discontinuing the IP will be immediately discontinued from study participation. The Investigator must report the pregnancy within 48 hours of learning of the pregnancy, to [REDACTED] Pharmacovigilance using the Pregnancy Data Collection Form via the same fax number and/or email address as for SAE reporting (see Section 11.2.6.1). The Investigator should contact the designated individual(s) who receive SAE notification and record information related to the pregnancy on an Exposure in Utero form provided by the sponsor or its designee.

Early Termination Visit assessments are required as soon as possible after learning of the pregnancy. The Investigator is also responsible for following the pregnancy until delivery or termination. These findings must be reported on the Exposure in Utero form and forwarded to the

designated individual(s). The event meets the SAE criterion only if it results in a spontaneous abortion or a congenital anomaly.

Male subjects with partners of childbearing potential should be advised to use contraception throughout their participation in the study. If the partner of a male subject becomes pregnant during his IP treatment or within 14 days of his discontinuing the IP, the Investigator must report the pregnancy within 48 hours of learning of the pregnancy, to [REDACTED] Pharmacovigilance, as described above.

## **12. DATA SAFETY MONITORING BOARD**

A data safety monitoring board will not be used in this study.

## 13. STATISTICS

An interim safety analysis will be performed when approximately 100 subjects have completed 12 months of PH94B dosing up to 4 times per day and approximately 300 subjects have completed 6 months of PH94B dosing up to 4 times per day. All subjects who have received at least 1 dose of PH94B at this point will be included in this analysis. A final analysis will be performed after the last subject has completed or discontinued from the study.

### 13.1. Statistical Analysis

This section presents a summary of the planned statistical analyses.

Safety, tolerability, and efficacy variables will be summarized using descriptive statistics. Descriptive summaries for categorical variables will include count and percentage. Descriptive summaries for continuous variables will include number of subjects (n), mean, standard deviation (SD), median, minimum, and maximum. Where appropriate, 95% confidence intervals (CIs) may be reported. Summaries will be presented by time point. All CIs will be 95%, unless stated otherwise.

Unless specified otherwise, all data recorded, will be listed by subject. A comprehensive description of planned analyses and statistical considerations will be described in the statistical analysis plan (SAP).

Summary statistics will be reported based upon observed data. Should a determination of treatment period be required for an AE or concomitant medication when the corresponding date is missing, or is a partial date, the event/medication will be considered as “on-treatment” unless the portions of the date that are available indicate that this is not possible.

Details of the planned analyses, including strategies if needed to assess and address consequences of the COVID-19 pandemic on study conduct and study data, will be provided in the SAP that will be finalized before the database is locked.

#### 13.1.1 Analysis Populations

A single analysis population is planned for this study:

- Safety population: All subjects who receive IP.

All analyses will be performed using the Safety population.

Primary and exploratory endpoints may be summarized by subgroups of interest including age, sex, concomitant medications, and SAD severity. Analysis of subgroups not pre-defined in the final SAP will be labeled as such in the clinical study report (CSR).

#### 13.1.2 Study Subjects and Demographics

##### 13.1.2.1 Disposition and Withdrawals

The numbers of subjects randomized, completing, and withdrawing, along with reasons for withdrawal, will be tabulated. Details on the number of subjects participating in the individual antecedent PH94B SAD studies will also be provided.

### **13.1.2.2 Protocol Deviations**

A protocol deviation is any noncompliance with the clinical study protocol or ICH GCP requirements. The noncompliance may be either on the part of the subject, the Investigator, or the study site staff. As a result of deviations, corrective actions are to be developed by the site and implemented promptly.

Documentation of the deviations and corrective actions will be included in the data quality assessment during review.

It is the responsibility of the site Investigator to use continuous vigilance to identify and report deviations within 2 working days of identification of the protocol deviation, or within 2 working days of the scheduled protocol-required activity. All deviations must be addressed in study source documents and reported to the sponsor. Protocol deviations must be sent to the reviewing IRB per their policies. The site Investigator is responsible for knowing and adhering to the reviewing IRB requirements. Further details about the handling of protocol deviations will be included in the protocol deviation guidance plan.

### **13.1.2.3 Demographics and Other Baseline Characteristics**

For all participating subjects, baseline is defined as Visit 2. For subjects who enter the present study within 14 days of their antecedent PH94B SAD study, Visit 2 assessments should be conducted as described in the schedule of events ([Table 2-1](#)). Demographics, medical and psychiatric history, MINI findings, SAD Diagnostic Criteria Checklists, and baseline characteristics such as gender, age, race, weight, height and baseline physical examination reports, and vital signs will be carried over.

Demographic variables will include age, sex, height, and weight. Information on race and ethnicity will be collected for any eventual analysis of differences in response to the IPs, in accordance with local regulatory requirements. Baseline subject characteristics will include medical and psychiatric history, MINI findings, and physical examination findings.

Prior and concomitant medications will be summarized, by the number and percentage of subjects taking each medication, classified using World Health Organization Drug Dictionary (WHO-DD) Anatomical Therapeutic Chemical (ATC) classes and preferred terms.

### **13.1.3 Exposure and Compliance**

Investigational product administration will be summarized in terms of total number of doses received and average number of daily doses.

Descriptive statistics will be provided overall and for each 3-month period of exposure (0-3 months, 4-6 months, 7-9 months, and 10-12 months).

### **13.1.4 Safety and Tolerability Analyses**

Safety analyses will be conducted using data from the safety population (as defined in [Section 13.1.1](#)). Safety variables include treatment-emergent AEs, clinical laboratory values, vital signs, changes in suicidality (C-SSRS), level of depression (HAM-D17), PWC-20 results, ECG readings, and physical examination results. No formal inferential analyses will be conducted for safety variables, unless otherwise noted.

The incidence of AEs for defined periods of exposure (e.g., 3 months, 6 months, 9 months, 12 months, and overall) will be evaluated in the form of a proportion relating number of subjects experiencing events to number of subjects at risk for AEs by organ, relatedness, severity of reported AE, and by frequency of AE. In addition, frequency-type of reported AEs (once, continuous, or adaptability to treatment) by time of occurrence after Visit 2 dispensation may be tabulated. These data will be summarized and tabulated, including CIs when appropriate, for descriptive purposes. Abnormal laboratory values, vital signs, 12-lead ECGs and findings from physical evaluations that are logged as AEs are included.

For each AE category (organ, relatedness, severity, frequency, etc.) the number of subjects reporting 1 or more AEs during the specified time period divided by the number of subjects exposed to the IP during that time period may serve as a nonparametric endpoint, and be subject to evaluation using time series analysis to investigate whether frequency of AEs changes with increased duration of exposure.

Descriptive statistics will be used to portray safety and tolerability of PH94B as measured by reports of AEs and SAEs, changes in laboratory values, 12-lead ECGs, physical examination, vital signs, and withdrawal symptoms.

Safety endpoints are as follows:

- Incidence and severity of AEs, AEs leading to discontinuation, and SAEs
- Changes in vital signs results
- Changes in clinical laboratory evaluation (hematology, chemistry, and urinalysis) results
- Changes in 12-lead ECG results
- Changes in physical examination findings
- Changes in HAM-D17 scores
- Changes in C-SSRS scores
- PWC-20 scores after termination of PH94B

#### 13.1.4.1 Adverse Events

All AEs will be coded using the most recent version of Medical Dictionary for Regulatory Activities (MedDRA).

Treatment-emergent AEs are defined as:

- AEs with onset at the time of or following the start of treatment with IP through the Follow-up Visit or Early Termination Visit, whichever occurs first, or
- AEs starting prior to the start of treatment but increasing in severity or relationship at the time of, or following, the start of treatment with IP through the Follow-up Visit or Early Termination Visit, whichever occurs first.

The number and percentage of subjects with AEs will be displayed by system organ class and preferred term. Summaries of AEs by severity and relationship to IP will also be provided. Serious adverse events and AEs resulting in discontinuation of IP will be summarized separately in a

similar manner. Subject listings of AEs, SAEs, and AEs causing discontinuation of IP will be produced.

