Subjects will be instructed to return to the clinic for Visit 3 after 30 days ( $\pm 3$  days). At Visit 3, subjects will undergo clinical laboratory assessments (clinical chemistry, hematology, urinalysis, pregnancy test, and urine drug screening), vital signs, 12-lead ECG, physical examination (limited to nasal passage and oropharynx examination unless any AEs are reported), HAM-D17, [REDACTED] LSAS, C-SSRS, CGI-S, CGI-I, and self-evaluation by the patient-reported outcome measure, Patient Global Impression of Change (PGI-C). At Visit 3, PH94B use and any daily reports of health problems that have been recorded in the eDiary application will be reviewed and AEs and concomitant medications will be reported and recorded. Subjects will receive a 1-month supply of PH94B.

Subjects will return to the clinic at monthly intervals ( $\pm 7$  days, Visits 4 to 13), and will repeat the same assessments as those performed at Visit 3. PH94B use and any daily reports of health problems that have been recorded in the eDiary application will be reviewed, AEs and concomitant medications will be reported and recorded at each visit. Subjects will receive a 1-month supply of PH94B at each monthly visit.

At Visit 14 (12 months $\pm$ 2 weeks), treatment will conclude, and subjects will undergo clinical laboratory assessments (clinical chemistry, hematology, urinalysis, pregnancy test, and urine drug screening), vital signs, 12-lead ECG, physical examination, HAM-D17, [REDACTED] LSAS, C-SSRS CGI-S, CGI-I, PGI-C, and the Penn Physician Withdrawal Checklist (PWC-20). Also, PH94B use and any daily reports of health problems that have been recorded in the eDiary application will be reviewed, and AEs and concomitant medications will be recorded and reported. Subjects will also be informed of their follow-up visit (Visit 15).

Subjects will return to the clinic for a follow-up visit (Visit 15, 54 weeks  $\pm$ 3 days), approximately 2 weeks after the last PH94B administration, to undergo C-SSRS, PWC-20, and vital signs assessments, and record AEs.

Subjects who discontinue study treatment without completing 12 months of treatment will attend an Early Termination Visit (Visit 14) as soon as possible after discontinuing treatment, and return to the clinic for a follow-up visit (Visit 15) approximately 2 weeks later.

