#### **11.1.5 Treatment-emergent Adverse Events**

Treatment-emergent AEs are defined as:

- AEs with onset at the time of or following the start of treatment with IP through the Follow-up Visit, or
- AEs starting prior to the start of treatment but increasing in severity or relationship at the time of, or following, the start of treatment with IP through the Follow-up Visit

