8.1. Adverse Events

Treatment emergent AEs (TEAEs) are defined as:

- AEs with onset at the time of or following the start of treatment with IP through final Visit or follow-up phone call.
- AEs starting prior to the start of treatment with IP but increasing in severity or relationship at the time of, or following, the start of treatment with IP through Visit 14 (End of Treatment/Follow-Up).
- AEs that occur between Visit 14 and Visit 15.

Any medical condition that is present at the time that the subject is screened will be considered as baseline and not reported as an AE. However, if the study subject's condition deteriorates at any time during the study, it will be recorded as an AE.

The Investigator will record all reportable events with start dates occurring any time after informed consent is obtained until 7 days after the last day of study participation. Events will be followed for outcome information until resolution or stabilization. Missing and partially missing start dates will be imputed for the purpose of analysis as described in Section **Error! Reference source not found.**

All AEs, TEAEs, and serious AEs (SAEs) will be coded using the MedDRA dictionary, as discussed in Section **Error! Reference source not found.**

All AE data will be categorized as Severe > Moderate > Mild. Relationship of all AEs to IP will be categorized as related or not related. In the summaries showing severity and relationship to study drug, the event with the maximum severity or strongest relationship to study drug will be reported. If a particular event is missing the severity and/or relationship, then the strongest possible severity or relationship will be assumed for analysis (severity = severe, relationship = related).

An overall summary of TEAEs will be provided; this will present number and percent of subjects who reported at least 1 of the following: TEAE (including any TEAE, TEAEs by maximum severity, and related TEAEs), TEAE leading to discontinuation of the study drug, TEAE leading to discontinuation from the study, serious TEAEs, and SAEs leading to death. TEAEs will be summarized by two time periods (TEAEs which occur prior to Visit 14 and those that occur during or after Visit 14).

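### The treatment-emergent AE window is defined inconsistently, and Protocol 13.1.4.1 closes it about two weeks sooner for early terminators than for completers

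*Protocol*

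**What the plan says.** Three current sections define the window.

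- **Protocol 11.1.5.** New-onset events count from "following the start of treatment with IP through the Follow-up Visit, or", and pre-treatment events that worsen count to the same visit. Completers and early terminators are not distinguished.
- **Protocol 13.1.4.1.** The same two event types count "through the Follow-up Visit or Early Termination Visit, whichever occurs first".
- **SAP 8.1.** There are three bullets. New-onset events count "through final Visit or follow-up phone call". Pre-treatment events that increase in severity or relationship count at or after "the start of treatment with IP through Visit 14 (End of Treatment/Follow-Up"). A third bullet adds "AEs that occur between Visit 14 and Visit 15".

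Protocol 7.1 gives the visit order. A subject who stops early "will attend an Early Termination Visit (Visit 14) as soon as possible after discontinuing treatment" and returns for Visit 15 about two weeks later. Protocol 10.2.4 has AEs reviewed and recorded at Visit 15. SAP Section 10 lists changes from the planned analysis and does not mention the TEAE definition.

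**The concern.** Protocol 6.3 puts AE incidence and severity first among the endpoints for the primary objective. Protocol 13.1.4 names TEAEs as the safety variable, and every AE summary table planned in SAP 12.3 is a TEAE table. In a single-arm descriptive study these counts are the main result, so the window should not depend on which section the programmer follows.

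The difference between the two protocol sections is also not neutral. It removes the off-drug fortnight after Visit 14/ET from one group of subjects, those who stopped early, and keeps it for those who finished.

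**Working it through.** There is no stated figure to reproduce. The sample size (up to 600) comes from an exposure guideline, and the documents give no dropout rate or AE rate. The check is therefore a comparison of the definitions, followed by an illustration of scale.

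**Step 1: visit order.** Protocol Table 2-1 puts Visit 14 at 52 weeks and Visit 15 at 54 weeks, and 54 − 52 = 2 weeks, as the text says. For an early terminator, Visit 14 is the ET Visit and Visit 15 follows about 2 weeks later. The ET Visit is always the earlier of the two. Protocol 10.2.3 separates the End of Treatment visit from the ET Visit, so a completer has no ET Visit and the earlier-of-two rule leads to Visit 15.

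**Step 2: last visit at which an event counts as treatment-emergent.**

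| Event and subject | Protocol 11.1.5 | Protocol 13.1.4.1 | SAP 8.1 |
|---|---|---|---|
| New onset, completer | Visit 15 | Visit 15 | Visit 15 |
| New onset, early terminator | Visit 15 | ET | Visit 15 |
| Worsening, completer | Visit 15 | Visit 15 | Visit 14 by bullet 2; Visit 15 if bullet 3 applies |
| Worsening, early terminator | Visit 15 | ET | Visit 14/ET by bullet 2; Visit 15 if bullet 3 applies |

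All three agree for new-onset events in completers. The two protocol sections differ in both early-terminator rows. The SAP sides with 11.1.5 on new onset and is unclear on worsening.

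**Step 3: why the SAP worsening rows are unclear.** Bullet 2 stops at Visit 14. Bullet 3 is not limited to new onset. Protocol 10.2.2.1 treats an aggravated event as a new AE, and SAP 8.1 records deterioration of a condition present at screening as an AE. On that reading bullet 3 catches worsening after Visit 14, and the limit in bullet 2 has no effect. The SAP does not say so. It also attaches a combined end-of-treatment and follow-up label to Visit 14 in bullet 2 and to Visit 15 later in 8.1 and in 8.1.2.

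**Step 4: scale, on assumptions.** Let N = 600, d = share terminating early, and p = probability of at least one AE in the fortnight after Visit 14/ET. Take p to be the same in both groups, and assume every early terminator attends Visit 15.

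- One window for all: N × p subjects, incidence p.
- Protocol 13.1.4.1: N × p × (1 − d) subjects, incidence p(1 − d).
- Subjects not counted: N × p × d.

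At p = 5%, one window gives 600 × 0.05 = 30 subjects.

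| d | Counted under 13.1.4.1 | Incidence for the period | Not counted |
|---|---|---|---|
| 10% | 30 × 0.9 = 27 | 4.5% | 3 |
| 30% | 30 × 0.7 = 21 | 3.5% | 9 |
| 50% | 30 × 0.5 = 15 | 2.5% | 15 |

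Over p = 2% to 10% and d = 10% to 50%, the number not counted runs from 600 × 0.02 × 0.1 = 1.2 to 600 × 0.10 × 0.5 = 30. These figures are for the fortnight only. The count of subjects with any TEAE over the whole study falls less, because some of them will have had an earlier TEAE.

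**The case against.** The strongest reply is that the SAP already handles this. Protocol 13.1 calls itself a summary and leaves the full description to the SAP. SAP bullet 3 counts events between Visit 14 and Visit 15, and because the ET Visit is Visit 14, early terminators are covered as completers are. This largely stands: if the SAP is run as written, the unequal treatment of new-onset events does not arise. It does not remove the conflict. The two protocol sections still contradict each other, no document states an order of precedence, and SAP Section 10 does not declare a departure from 13.1.4.1.

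A reader might go further than the documents allow in four ways.

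- *All AEs after stopping are lost in early terminators.* They are not. Off-drug days before the ET Visit count under every definition. Later events are still to be recorded under Protocol 11 and 11.2 and listed. Only the treatment-emergent label is affected.
- *The SAP rescues new-onset events only.* This is not established, for the reason in Step 3 of the working.
- *The excluded subjects mostly stopped because of AEs, so the bias is large.* The documents do not give reasons for stopping. Protocol 5.2.2 reports no AE-related terminations in the acute-dosing Phase 2 studies.
- *Withdrawal effects would go unseen.* The PWC-20 is collected at Visits 14 and 15 and does not depend on the TEAE window.

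It can also be said that the follow-up phone call in SAP bullet 1 is harmless, since the final visit is Visit 15. That is probably so, but no such call is in the visit schedule and the phrase recurs in SAP 8.4.

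**Conclusion.** The inconsistency is real and sits in current text. Protocol 11.1.5 and 13.1.4.1 cannot both be followed for early terminators. Under 13.1.4.1, roughly two weeks of follow-up after Visit 14/ET feeds the TEAE tables for completers and not for early terminators. SAP 8.1 mostly closes that gap but leaves worsening pre-treatment events ambiguous.

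The practical effect depends on which section is applied, and the documents do not give its size. The illustrative drop from 5% to between 4.5% and 2.5% for the fortnight rests on an assumed AE risk, assumed early termination of 10% to 50%, equal risk in both groups, and full attendance at Visit 15. Missed Visit 15s would make the loss smaller. No hypothesis test is involved, so what is at stake is a clear and reproducible safety count.

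**What to change.** Put one definition in Protocol 11.1.5, Protocol 13.1.4.1 and SAP 8.1: onset or worsening from the first dose of investigational product through Visit 15, applied identically to completers and early terminators. To get there:

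1. In Protocol 13.1.4.1, delete the ET alternative and the earlier-of-two condition from both bullets.
2. In SAP 8.1, delete the phone-call wording from bullet 1 and the Visit 14 limit from bullet 2. Bullet 3 is then redundant.
3. Reconcile the AE recording period, which is 14 days after last participation in Protocol 11 and 11.2 and 7 days in SAP 8.1.

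The cost is wording in the two documents. TEAE counts may rise slightly compared with 13.1.4.1 as written.
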